	
 • Sequential comparison of MAP blood PCR assay results per subject • Proportion of enrolled subjects with a MAP positive blood culture at baseline (week 0 of the open label phase). • Proportion of subjects with a change in MAP blood culture status after 26 weeks of treatment compared to baseline (week 0 of the open label phase). • Proportion of subjects with a change in MAP blood culture status after 52 weeks of treatment compared to baseline (week 0 of the open label phase). 
Endoscopic Changes in Those Subjects Who Undergo Colonoscopy:
 
 • Change from baseline in the mean Crohn's Disease Endoscopic Index of Severity (CDEIS) after 16 and 52 weeks of treatment • Change from baseline in the mean Simple Endoscopic Activity Score (SES-CD) after 16 and 52 weeks of treatment • Success rates of (ΔCDEIS and SES-CD) defined by 25% and 50% improvements • Correlation between the change from baseline in the endoscopic index (ΔCDEIS) and the clinical index (ΔCDAI) after 16 and 52 weeks of treatment • Comparison of success rates of (ΔCDEIS) defined by 25% and by 50% improvements in CDEIS vs CDAI defined remission • Comparison of success rates of (ΔCDEIS) defined by 25% and by 50% improvements in CDEIS vs CDAI defined response • Correlation between the change from baseline in the endoscopic index (ΔSES-CD) and the clinical index (ΔCDAI) after 16 and 52 weeks of treatment • Comparison of success rates of (ΔCDEIS) defined by 25% and by 50% improvements in SES-CD vs CDAI defined remission • Comparison of success rates of (ΔCDEIS) defined by 25% and by 50% improvements in SES-CD vs CDAI defined response 
Health-Related Quality-of-life (HRQoL):
 
 • Change from baseline (initiation of open label phase) in the SF-36 questionnaire total score and domain scores to 16, 26 and 52 weeks. • Change from baseline (initiation of open label phase) in the mean Inflammatory Bowel Disease Questionnaire (IBDQ) score to 16, 26, and 52 weeks. 
Inflammation:
 
 • Changes from baseline in a serum marker of inflammation: C-reactive Protein (CRP) • Changes from baseline in a stool marker of inflammation: fecal calprotectin 
Safety: The incidence of adverse events during the study and changes from baseline in vital signs, Clostridium difficile toxin, ECG, hematology and chemistry laboratory parameters

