2.1.4 Selected Other Objectives

MAP Detection:

1. To estimate the proportion of subjects with a MAP positive blood PCR assay at baseline (week 0 of the open label phase).
2. To estimate the proportion of subjects with a change in MAP blood PCR assay status after 16 weeks of treatment compared to baseline (week 0 of the open label phase).
3. To estimate the proportion of subjects with a change in MAP blood PCR assay status after 52 weeks of treatment compared to baseline (week 0 of the open label phase).
4. To make sequential comparisons of MAP blood PCR assay results per subject.
5. To estimate the proportion of enrolled subjects with a MAP positive blood culture at baseline (week 0 of the open label phase).
6. To estimate the proportion of subjects with a change in MAP blood culture status after 26 weeks of treatment compared to baseline (week 0 of the open label phase).
7. To estimate the proportion of subjects with a change in MAP blood culture status after 52 weeks of treatment compared to baseline (week 0 of the open label phase).

Because the buffy coat is the actual component of blood that is cultured, MAP blood culture should be considered equivalent to MAP buffy coat culture. Because the development of a MAP

blood PCR assay is still in progress, MAP detection objectives 1-4 will comprise the contents of a later report and will not be addressed in tables, listings, or figures of this clinical study report.

Endoscopic Changes in Those Subjects Who Undergo Colonoscopy:

8. To estimate the change from baseline in the mean Crohn's Disease Endoscopic Index of Severity (CDEIS) after 16 and 52 weeks of treatment).
9. To estimate the change from baseline in the total Simple Endoscopic Activity Score weeks (SES-CD) after 16 and 52 weeks of treatment.
10. To make a comparison of success rates of (Δ CDEIS and SES-CD) defined by 25% and 50% improvements.
11. To estimate the correlation between the change from baseline in the endoscopic index (Δ CDEIS) and the clinical index (Δ CDAI) after 16 and 52 weeks of treatment.
12. To make a comparison of success rates of (Δ CDEIS) defined by 25% and 50% improvements and CDAI defined remission.
13. To make a comparison of success rates of (Δ CDEIS) defined by 25% and 50% improvements and CDAI defined response.
14. To make a comparison of success rates of (Δ SES-CD) defined by 25% and 50% improvements and CDAI defined remission.

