2.2.4.2 Endoscopic Change Endpoint/Variables

- Change from baseline to week 16 and 52 in Crohn's Disease Endoscopic Index of Severity (CDEIS) and Simple Endoscopic Score for Crohn's Disease (SES-CD). The CDEIS and SES-CD are endoscopic scoring systems for the assessment of CD.
- Success rate by 25% improved in CDEIS from baseline to week 16 and 52. Success is achieved if the CDEIS score is decreased by 25%.
- Success rate by 50% improved in CDEIS from baseline to week 16 and 52. Success is achieved if the CDEIS score is decreased by 50%.
- Success rate by 25% improved in SES-CD from baseline to week 16 and 52. Success is achieved if the SES-CD score is decreased by 25%.
- Success rate by 50% improved in SES-CD from baseline to week 16 and 52. Success is achieved if the SES-CD score is decreased by 50%.
- Comparison of success rate of by 25% and 50% improved in CDEIS from baseline to week 16 and 52 vs CDAI defined remission.
- Comparison of success rate of by 25% and 50% improved in CDEIS from baseline to week 16 and 52 vs CDAI defined response.
- Comparison of success rate of by 25% and 50% improved in SES-CD from baseline to week 16 and 52 vs CDAI defined remission.
- Comparison of success rate of by 25% and 50% improved in SES-CD from baseline to week 16 and 52 vs CDAI defined response.

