6.3.4.2 Endoscopic Assessment Based on CDEIS and SES-CD

The Crohn's Disease Endoscopic Index of Severity (CDEIS) is a validated quantitative measure of disease severity upon endoscopy. The score ranges from 0-44 based upon the extent and severity of inflammation and ulcers seen during endoscopy of the colon. A response is a decrease in score from baseline.

The Simple Endoscopic Score for Crohn's Disease (SES-CD) is a validated quantitative measure of disease severity upon endoscopy that is based on four endoscopic variables (presence and size of ulcers, extent of ulcerated surface, extent of affected surface, and presence of narrowing). Each

variable is assessed in each of the five ileocolic segments: rectum, sigmoid and left colon, transverse colon, right colon, and ileum. Each of the four SES-CD variables is scored from 0 to 3, with the sum of the scores for each variable ranging from 0 to 15 (Total SES-CD score range 0–60).

CDEIS data are presented in data listing only.

The SES-CD total scores by visit (baseline and weeks 16 and 52) and change from baseline scores to week 16 and 52 will be summarized descriptively for subjects who consent to undergo colonoscopy by parent study treatment and overall. The summary statistics include number of observations, mean with 95% CI, standard deviation, median, inter-quartile ranges, minimum, and maximum.

Number and proportion of subjects who achieved success defined below and corresponding 95% exact Clopper-Pearson CI for the proportion will be provided.

- by 25% improved in SES-CD from baseline to week 16 and 52. Success is achieved if the SES-CD score is decreased by 25%.
- by 50% improved in SES-CD from baseline to week 16 and 52. Success is achieved if the SES-CD score is decreased by 50%.

Paired response between each of above defined improvement and corresponding CDAI remission (<150) at each visit will be compared using exact McNemar’s test. Similarly, paired response between each of above defined improvement and corresponding CDAI response (≥100% decrease from baseline) at each visit will be compared using exact McNemar’s test.

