6.5 Changes to Statistical Analysis Methods Planned in the Protocol

Because the buffy coat is the actual component of blood that is cultured, MAP blood culture should be considered equivalent to MAP buffy coat culture. Because the development of a MAP blood PCR assay is still in progress, MAP detection objectives 1-4 will comprise the contents of a later report and will not be addressed in tables, listings, or figures of this clinical study report.

Change from baseline in the Short Form-36 Health Survey (SF-36) total score have been removed to be consistent with parent study. Summary of domains are removed in SAP.

Correlations between the change from baseline in SES-CD and the change from baseline in CDAI to week 16 and 52 are not included in SAP.

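### The planned McNemar tests compare endoscopic and CDAI success rates but do not estimate whether the same subjects succeed on both, and the protocol's correlation outcomes have no analysis

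*SAP*

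**What the plan says.** SAP 6.3.4.2 defines SES-CD success as a 25% or a 50% fall from baseline at weeks 16 and 52. Each success rate gets a Clopper-Pearson interval. The link to the clinical index is then made by McNemar's test, which the sentence goes on to name: "Paired response between each of above defined improvement and corresponding CDAI remission (<150) at each visit will be compared using exact". It is also the method for response, again named at the end of the sentence: "paired response between each of above defined improvement and corresponding CDAI response (≥100% decrease from baseline) at each visit will be compared using exact". No agreement measure, conditional proportion or correlation is named.

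The matching endpoint in SAP 2.2.4.2 reads "Comparison of success rate of by 25% and 50% improved in SES-CD from baseline to week 16 and 52 vs CDAI defined remission", with parallel entries for response and for CDEIS.

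The protocol also asks about association. Its Outcome Measures include "Correlation between the change from baseline in the endoscopic index (ΔSES-CD) and the clinical index (ΔCDAI) after 16 and 52 weeks of treatment" and the same item for CDEIS. Only the CDEIS version is also a protocol objective.

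In the SAP the two correlations fare differently:

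- **SES-CD.** Section 6.5 states: "Correlations between the change from baseline in SES-CD and the change from baseline in CDAI to week 16 and 52 are not included". No reason is given, whereas the removal of the SF-36 total score, in the same section, is explained by consistency with the parent study.
- **CDEIS.** Section 2.1.4 keeps it as objective 11 ("To estimate the correlation between the change from baseline in the endoscopic index", there meaning CDEIS). Section 2.2.4.2 has no correlation endpoint, 6.3.4.2 confines CDEIS to a listing, and 6.5 does not mention CDEIS.

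**The concern.** McNemar's test uses only the discordant pairs: subjects who succeed on SES-CD but not CDAI, and the reverse. It tests whether the two marginal success rates are equal. The concordant cells, which show whether the same people do well on both measures, do not enter the p-value.

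The CDAI depends partly on what subjects report in a diary, and treatment here is open label. Whether subjects counted as CDAI remitters also improve endoscopically is therefore a natural question, and the protocol's correlations pose a version of it. With those gone, the only planned output that links endoscopic change to CDAI outcome is a p-value for a different question. A large p-value could be misread as agreement and a small one as conflict.

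**Working it through.** **The plan's own figure.** The only design figure is in SAP 6.1.7: a maximum Clopper-Pearson width of 0.203 with 100 patients. At 50/100 the limits are 0.3983 and 0.6017, width 0.2034, so it reproduces. It does not bear on this point, and the precision it describes is for 100 subjects, not for those who consent to colonoscopy.

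**Inputs.** The documents give neither the number having colonoscopy nor any expected success rates. The tables below are therefore assumptions that show how the test behaves; they are not predictions.

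**Notation.** a = success on both, b = SES-CD only, c = CDAI only, d = neither, n = a+b+c+d.

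- Exact McNemar p: two-sided binomial probability for b out of b+c at 0.5. If b = c, p = 1.0.
- Agreement: po = (a+d)/n.
- Chance agreement: pe = [(a+b)(a+c) + (c+d)(b+d)]/n².
- Kappa = (po - pe)/(1 - pe).

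**Case 1: equal rates, n = 40, 12 successes on each measure.** With overlap a, b = c = 12 - a and d = 16 + a. Then pe = (12×12 + 28×28)/1600 = 928/1600 = 0.58 and po = (16 + 2a)/40.

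| Overlap a | b = c | d | McNemar p | Agreement | Kappa | SES-CD success in CDAI remitters | in non-remitters |
|---|---|---|---|---|---|---|---|
| 0 | 12 | 16 | 1.0 | 40% | -0.43 | 0/12 | 12/28 |
| 4 | 8 | 20 | 1.0 | 60% | 0.05 | 4/12 | 8/28 |
| 6 | 6 | 22 | 1.0 | 70% | 0.29 | 6/12 | 6/28 |
| 9 | 3 | 25 | 1.0 | 85% | 0.64 | 9/12 | 3/28 |
| 12 | 0 | 28 | 1.0 | 100% | 1.00 | 12/12 | 0/28 |

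The p-value is the same in every row; the last four columns are not. Equal margins force b = c, so p = 1.0 holds at any n. With both rates at 50%, kappa of 1, 0 and -1 all give p = 1.0 at n = 20, 40, 60 and 100.

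**Case 2: every CDAI remitter also improves, n = 40.** Take a = 10, b = 10, c = 0, d = 20. Then p = 2 × 0.5^10 = 0.002. Agreement is 30/40 = 75%, pe = (20×10 + 20×30)/1600 = 0.50, and kappa = 0.25/0.50 = 0.50. The test is clearly significant although SES-CD success occurs in 10/10 remitters, against 10/30 non-remitters.

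**Precision of the alternative.** For 12/12 the exact 95% lower limit is 0.025^(1/12) = 0.735; for 0/12 the upper limit is 1 - 0.735 = 0.265. For 4/12 the interval is 0.10 to 0.65. Extremes would be told apart; intermediate results would be imprecise.

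**Is the gap filled elsewhere?** The endoscopy tables in SAP 8.1 (14.2.6.1 to 14.2.6.3) cover SES-CD scores and the 25% and 50% reductions. No title names a cross-tabulation with CDAI or the McNemar results. The logistic models in 6.3.1 and the related subgroup tables use baseline SES-CD within a composite, not its change.

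**The case against.** The strongest reply is that McNemar's test does what the documents ask. SAP objectives 12 to 15 and section 2.2.4.2 speak of comparing success rates, and a paired comparison of rates is McNemar's purpose. No objective mentions agreement. This stands: a reader might infer that the wrong test was chosen, and the documents do not support that. The gap is an additional question left without an analysis.

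A reader might also infer that the SES-CD correlation was dropped silently. It was not: 6.5 is the section for changes from the protocol, and 6.1.1 lets the SAP supersede it. Only the reason is missing. For the CDEIS correlation the criticism is stronger, because objective 11 remains and its loss is not declared.

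A third tempting inference is that nothing in the plan checks CDAI remission against an objective measure. SAP 6.3.3.2 reports remission combined with a 50% fall in CRP or calprotectin at weeks 16 and 52. That is a within-subject joint outcome and is not confined to the colonoscopy subset. It is not endoscopic, but it answers part of the worry.

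Section 8 places table layouts in a separate document, so the 2x2 cells may yet be shown. If they are, agreement and conditional proportions can be read off. The SAP does not commit to this, and does not promise intervals.

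Kappa also depends on the margins: in Case 2 it is only 0.50 although every remitter improved. Hence kappa is optional in the fix and the conditional proportions come first.

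**Conclusion.** The point holds in a limited form. The McNemar tests are valid for comparing the two success rates, but no planned analysis estimates how endoscopic change relates to CDAI outcome within subjects. The protocol's two correlation outcomes have no analysis: one is removed openly but without a reason, and the other survives as an objective with only a data listing behind it.

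The size of the problem is shown by illustration: p = 1.0 with kappa anywhere from -0.43 to 1.00, and p = 0.002 with all remitters improving. The counts are assumed. What does not depend on them is that equal margins give p = 1.0 whatever the overlap.

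The consequence is small. These are selected other endpoints, the lowest of the four families in SAP 2.2, measured in subjects who consent to colonoscopy. The primary remission estimate does not change.

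**What to change.** 1. In SAP 6.3.4.2, keep exact McNemar's test for the comparison of rates.
2. For each SES-CD threshold against CDAI remission and CDAI response, at weeks 16 and 52, add the 2x2 table with percent agreement. Add the proportion with SES-CD success among subjects who met the CDAI criterion and among those who did not. Give exact 95% CIs and state the denominator. Kappa with a 95% CI is optional.
3. Reinstate the Spearman correlation of change in SES-CD with change in CDAI at weeks 16 and 52, with 95% CI.
4. Either analyse objective 11 or declare its removal in 6.5 with a reason. The listing-only rule also affects the other CDEIS objectives, so the declaration should cover whatever is dropped.
5. Before the response comparison is run, reconcile the percentage wording of CDAI response in 6.3.4.2 with the reduction of at least 100 in CDAI score in 2.2.2.

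The cost is a few lines of SAP text and one more table, from data already collected. The intervals will be wide in a consenting subset, and the table should be labelled exploratory.

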Study Population:	
Active subjects in the RHB-104-01 A Phase III Randomized, Double Blind, Placebo-controlled, Multicenter, Parallel Group Study to Assess the Efficacy and Safety of Fixed-dose Combination RHB-104 in Subjects with Moderately to Severely Active Crohn's Disease (MAPUS) study with CDAI of greater than or equal to 150 despite 26 weeks of treatment with investigational drug.
 
The following inclusion criteria apply:
 
 • Participation in RHB-104-01 for: 
 ○ 26 weeks, and a Crohn's Disease Activity Index (CDAI) score of ≥ 150 at Visit Week 26 OR ○ More than 26 weeks, with a CDAI ≥ 150 at Visit Week 26 and all subsequent visits, and subject is between Week 26 and 52 within 4 weeks (28 days) of site activation • White blood cell count $\geq 3.5 \times 10^9$ at screening. • Subject agrees to use the following effective contraceptive methods 
 ○ diaphragm, cervical cap, contraceptive sponge or condom with spermicidal foam/gel/cream/suppository ○ IUD/IUS ○ progestogen injection (Depo-Provera®) 
throughout the study and for at least 6 weeks after last study drug administration, unless subject or partner of subject is post-menopausal or otherwise incapable of becoming pregnant by reason of surgery or tubal ligation, or has had a vasectomy. In regions where local regulatory contraceptive requirements differ, the ICF will reflect local policies
 
The following key exclusion criteria apply:
 
 • Treatment with any medication that causes QT prolongation or Torsades de Pointes, including but not limited to: amiodarone, amitriptyline, astemizole, cisapride, citalopram dose greater than 20 mg/day, dihydroergotamine, disopyramide, dofetilide, dronedarone, ergotamine, ibutilide, ondansetron or other 5-HT₃ receptor antagonists, pimozide, procainamide, quinidine, quinine, quinolones, ranolazine, risperidone, sotalol, terfenadine and tolteridine. QT prolonging drugs may be referenced at the CredibleMeds® web site: https://crediblemeds.org/index.php/drugsearch • Treatment with the following CYP3A4 interactive medications: alfentanil, alprazolam, amlodipine, anti-retroviral agents, apixabin, aprepitant, aripiprazole, atorvastatin, boceprevir, buspirone, carbamazepine, carvedilol, colchicine, cyclosporine, digoxin, diltiazem, estrogens, felodipine, fluconazole, fluvoxamine, grapefruit juice, haloperidol, ketoconazole, lovastatin, lurasidone, metoprolol, nefazodone, nifedipine, nisoldipine, nitrendipine, propranolol, roflumilast, simvastatin, St. John's wort, and voriconazole. • Positive stool results for C. difficile. • Currently diagnosed or history of uveitis confirmed by either an ophthalmologist or

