RHB-104-01 Study Drug	WK 1	WK 2	WK 3	WK 4	WK 5-36														
Placebo	1 capsule RHB-104 + 4 capsules PBO Bid	2 capsules RHB-104 + 3 capsules PBO bid	3 capsules RHB-104 + 2 capsules PBO bid	4 capsules RHB-104 + 1 capsules PBO bid	5 capsules RHB-104 bid														
RHB-104	5 capsules RHB-104 Bid	5 capsules RHB-104 bid	5 capsules RHB-104 bid	5 capsules RHB-104 bid	5 capsules RHB-104 bid														
Outcome Measures	
Remission (primary outcome measure) – Remission in a subject is defined as a CDAI score of <150 at 16 weeks.
 
Response – A response in the individual subject is defined as reduction in CDAI score of ≥100 from baseline where baseline is the measure taken at Screening of this trial (Visit Week 26 of RHB-104-01).
 
Time to remission – The time (weeks after initiation) that a subject first records a state of remission.
 
Duration of remission – The time that a subject is in a state of remission.
 
Time to response – The time (weeks after initiation) that a subject first achieves a state of response.
 
Duration of response – The time that a subject is in a state of response.
 
Maintenance of Remission – Remission in a subject from week 16 through week 52.
 
Other Outcome Measures
 
MAP Detection:
 
 • Proportion of subjects with a MAP positive blood PCR assay at baseline (week 0 of the open label phase). • Proportion of subjects with a change in MAP blood PCR assay status after 16 weeks of treatment compared to baseline (week 0 of the open label phase). • Proportion of subjects with a change in MAP blood PCR assay status after 52 weeks of treatment compared to baseline (week 0 of the open label phase). 																		

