2.1.2 Secondary Objective

The secondary objective is to estimate the response rate of patients, defined by a reduction of CDAI score of ≥ 100 points at week 16 after the initiation of the open-label phase.

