2.2.2 Key Secondary Endpoint/Variable

The key secondary variable is the proportion of subjects who experienced response at week 16 after initiation, where response is defined as reduction from baseline of ≥ 100 in CDAI score. Subjects who have a change from baseline to week 16 in CDAI score which is not a reduction of ≥ 100 or who do not have a change from baseline to week 16 in CDAI score will be classified as not having experienced response at that time point.

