2.2.3 Selected Other Secondary Endpoints/Variables

- Time to remission – Number of weeks after initiation that a subject first records a state of remission (CDAI score < 150). It will be calculated as the date on which remission is first observed minus the date of the first dosing date plus 1 day, divided by 7. For subjects still on study and not achieved remission at the time of assessment, time to remission will be censored at the date of the last assessment of CDAI score.
- Duration of remission – The number of weeks the subject is in remission (CDAI score < 150). It will be calculated as the first date following remission at which CDAI is ≥ 150 minus the date of remission, plus 1 day, divided by 7. Those subjects who experienced remission and continue to be in remission at the time of their last CDAI assessment will be censored at the date of their last CDAI assessment. Duration of remission will be calculated only for patients achieving remission.
- Time to response – Number of weeks after initiation that a subject first achieves a state of response (a reduction from baseline of ≥ 100 in CDAI score). It will be calculated as the date on which response is first observed minus the date of the first dose, plus 1 day, divided by 7. For those subjects who have not experienced response, time to response will be censored at the date of the last assessment of CDAI score.
- Duration of response – Time in weeks that a subject is in a state of response (a reduction from baseline of ≥ 100 in CDAI score). It will be calculated as the first date following response at which the reduction from baseline in CDAI is < 100 minus the date of response, plus 1 day, divided by 7. Those subjects who experienced response and continue to be in response at the time of their last CDAI assessment will be censored at the date of their last CDAI assessment. Duration of response will be calculated only for patients achieved response.
- Proportion of subjects experienced maintenance of remission (CDAI score < 150) from week 16 through week 52. Subjects experiencing a CDAI score ≥ 150 at any visit time point assessment between week 16 and week 52 or have no CDAI measurement week 16 or week 52 will be considered as having not achieved maintenance of remission.

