6.1.3 Missing Data and Handling of Dropouts

All available outcome and safety data will be included in data listings and tabulations.

CDAI Missing Data:

The computation of CDAI requires 7 days of consecutive diary daily data. For subjects with CDAI diary data reported that is less than 7 days of data, the reported data will be standardized to 7 days by dividing the sum of CDAI score over the number of days of data by total number of days of reported data multiplied by 7. If less than 4 days of diary data is available, the subject will be categorized as a non-responder and the CDAI score will be considered missing. As specified in section 2.2, subjects with missing assessment will be assumed to not be in a state of remission/success for each scheduled visit (week 16, 26, or 52).

Handling of missing date information for AEs:

The term *missing date* refers to a completely missing date or to partial date where month or/and day or/and year is/are missing, e.g. missing month/day/year. Missing start and end dates will be imputed conservatively, i.e. missing values will be imputed in such a way that the duration of the AE is considered with the longest possible duration. The missing start date and end date of AE will be imputed for the purpose of defining treatment emergent adverse events (TEAE) and for assigning events to treatment periods using the following definitions:

(i) Adverse Event Start Date:

Event Missing Day: If Adverse event day is missing but month and year present, then impute the 1st of the month unless month and year are the same as first dose of study drug then impute day first day of dose.

Event Missing day and month – If adverse event day and month both are missing but year is present then impute 1st January unless year is the same as first dose date then impute day and month first dose day and month.

Completely missing – impute first dose date unless the end date suggests it could have started prior to this in which case impute the 1st January of the same year as the end date.

(ii) Adverse Event End Date:

Missing day – If AE day is missing but month and year is present then impute the last day of the month.

Missing day and month – If AE has missing day and month but year is present then impute 31st December.

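### SAP 6.3.4.2 sets the CDAI-response cut-off for the SES-CD McNemar tests at a 100% fall instead of a 100-point fall, a level essentially no subject can reach

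*SAP*

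**What the plan says.** SAP 6.3.4.2 defines SES-CD success as a 25% or a 50% decrease from baseline, assessed at weeks 16 and 52. It pairs each success indicator first with CDAI remission (below 150) and then with CDAI response, using the exact McNemar test. For the second pairing the operative words are "corresponding CDAI response (≥100% decrease from baseline) at each visit will be compared using exact".

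Elsewhere response is an absolute change in the score:

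- SAP 2.1.2, secondary objective: "defined by a reduction of CDAI score of ≥ 100 points at week 16". The protocol synopsis gives the same threshold under Objectives.
- SAP 2.2.2, key secondary endpoint: "where response is defined as reduction from baseline of ≥ 100 in CDAI score".
- SAP 2.2.3, time to response: "first achieves a state of response (a reduction from baseline of ≥ 100 in CDAI score". Duration of response uses the same threshold.
- Protocol synopsis, Outcome Measures: "A response in the individual subject is defined as reduction in CDAI score of ≥100 from baseline".

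SAP 2.2.4.2, which lists the endpoint behind these tests, gives no separate threshold. It says only "improved in SES-CD from baseline to week 16 and 52 vs CDAI defined response". SAP 6.5, which lists departures from the protocol's methods, mentions no percentage-based response.

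**The concern.** The parenthetical in 6.3.4.2 is the only definition of response in the section a programmer would work from. It does not look out of place there. The success criteria just above it are percentages, and the preceding sentence gives the remission cut-off in the same bracketed form, correctly. SAP 6.1.1 also says the SAP prevails over the protocol where their statistical methods disagree, so the protocol's definition does not clearly override it.

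If the text is followed literally, almost nobody is a CDAI responder in these tests. McNemar's test compares two marginal proportions through the discordant pairs. With one margin empty, it only asks whether the number of endoscopic successes differs from zero. SAP objective 15, which compares SES-CD success rates with CDAI-defined response, would then go unanswered, although the output would look like a valid test with a p-value.

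**Working it through.** **Inputs from the documents.** Entry requires "CDAI of greater than or equal to 150 despite 26 weeks of treatment" (protocol synopsis, Study Population). The protocol takes the CDAI baseline for response from that screening measurement. The response threshold is 100 points (SAP 2.1.2, 2.2.2, 2.2.3; protocol Outcome Measures and Objectives). SES-CD cut-offs are 25% and 50%, at weeks 16 and 52 (SAP 6.3.4.2). The documents give neither a CDAI distribution nor the size of the colonoscopy subset, so baselines above 150 and all counts below are assumptions.

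**Step 1: can the 100% figure be derived from the plan's own definition?** A 100-point fall as a percentage of baseline B is 100 × 100/B. It equals 100% only at B = 100, which is below the entry minimum. The two rules therefore differ for every eligible subject.

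| Baseline CDAI | 100-point rule: visit CDAI needed | As % decrease | 100% rule: visit CDAI needed |
|---|---|---|---|
| 150 (entry minimum) | 50 or less | 66.7% | 0 or less |
| 250 (assumed) | 150 or less | 40.0% | 0 or less |
| 300 (assumed) | 200 or less | 33.3% | 0 or less |
| 450 (assumed) | 350 or less | 22.2% | 0 or less |

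**Step 2: number of comparisons.** 2 SES-CD cut-offs × 2 visits = 4 tests against CDAI response. SAP 6.3.4.2 does not say whether they are repeated by parent-study treatment; if they are, the count rises.

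**Step 3: the test under the literal rule.** Let b be the subjects with SES-CD success but no CDAI response, and c the reverse. With no CDAI responders, c = 0 and b = k, the number of SES-CD successes. The two-sided exact p-value is then 2 × 0.5^k:

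- k = 3: 0.25
- k = 5: 0.0625
- k = 6: 0.031
- k = 12: 0.0005

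The direction is forced. Significance is not, since it depends on k alone.

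**Step 4: the same test under the 100-point rule.** Hold SES-CD successes at 12 (assumed) and vary the assumed numbers of responders and of subjects meeting both criteria. Then b = 12 − both, c = responders − both, and p is the two-sided exact binomial probability on b + c pairs.

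| Responders | Both | b vs c | p |
|---|---|---|---|
| 4 | 2 | 10 vs 2 | 2 × (1 + 12 + 66)/4096 = 0.039 |
| 8 | 4 | 8 vs 4 | 2 × (1 + 12 + 66 + 220 + 495)/4096 = 0.39 |
| 12 | 6 | 6 vs 6 | 1.00 |
| 16 | 7 | 5 vs 9 | 2 × (1 + 14 + 91 + 364 + 1001 + 2002)/16384 = 0.42 |

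Under the literal rule all four rows give 12 vs 0 and p = 0.0005. In the last row the direction is reversed as well.

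**The case against.** The strongest reply is that this is a slip that would correct itself. Response is defined consistently elsewhere in the SAP, the endpoint in 2.2.4.2 defers to that definition, and Listing 16.2.6.2 implies that response variables will already have been derived. A programmer would probably reuse them. If not, a nearly empty responder column at week 16 would sit oddly beside the key secondary table (14.2.2) and might be noticed. The tests are also low in the hierarchy: they use only subjects who consent to colonoscopy, and no table title in SAP section 8.1 names a McNemar test or a comparison with CDAI response.

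Much of this stands. It limits the consequence and makes literal programming a risk, not a certainty. It is also true that the p-values in Step 4 rest on invented counts, that McNemar's test does not measure agreement under either rule, and that the missing-data and rescue-medication analysis rules already apply to response in general terms.

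It does not remove the error. The threshold is wrong in the section that specifies the analysis. Even with the right flag, the output would not match the written plan, and a reader of the SAP could not tell which rule had been used. The argument that the threshold is unreachable needs none of the assumed counts; it follows from the entry criterion alone.

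**Conclusion.** The concern holds: the threshold in SAP 6.3.4.2 is wrong as written. It contradicts every other definition of response in both documents and requires a CDAI of 0 or below, whereas the intended 100-point fall is never more than 66.7% of an eligible baseline. Four McNemar comparisons are affected, on the assumption that they are run overall only.

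The claim that essentially no subject would qualify is a judgement from the size of the required fall (at least 150 points, down to zero or less), because the documents give no CDAI distribution. The p-values show the mechanism and do not forecast results.

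The primary, key secondary, time-to-event and remission McNemar analyses carry their own correct definitions and are not affected. The correction should be made because it is free and the written rule defeats the purpose of these tests, but it does not bear on the trial's main conclusions.

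**What to change.** In SAP 6.3.4.2, replace the percentage threshold with a decrease from baseline of at least 100 CDAI points, cross-referring to 2.2.2. Section 2.2.2 is worded for week 16, so state that the same threshold applies at week 52; the definition in 2.2.3 is not tied to a visit and can be cited for this.

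Add one sentence saying that these tests use the same response flag as the other response analyses. That brings in the existing missing-data rules of 2.2.2 (week 16) and 6.1.3 (weeks 16 and 52), the latter being that "subjects with missing assessment will be assumed to not be in a state of remission/success for each scheduled visit", and the existing rescue-medication analysis rule of 2.2.1 and 6.1.6. No new rule is needed. If programming has begun, confirm which definition was coded.

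The cost is one phrase and a cross-reference, with no effect on data collection or trial conduct.
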